3.7.1.3 Prospective Phase (6 Months)

The prospective phase is 6 months from the baseline visit (Day 1) to the Month 6/ET visit. Subjects will have their final assessment visit at Month 6/ET. Monthly assessments will follow a 28-day schedule.

In the event a scheduled assessment period visit is missed by a subject, the trial site will contact the subject immediately and reschedule another visit as close to the original visit schedule date as possible. After at least 2 phone calls are attempted, a certified letter will be sent to the subject. If a rescheduled visit falls outside of the allowable time window, then the investigator will contact the sponsor (or designee) to determine whether the subject can continue in the trial and to obtain approval to continue or discontinue the subject.

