3.7.1.3.2 Months 1 and 2 Visits

At the Months 1 and 2 visits (- 3/ + 2 days), the following will be performed:

- Abilify MyCite products (aripiprazole tablet embedded with an IEM sensor), supplies, and patches (prescribed dose is recorded) sufficient for 1 month will be dispensed. Any treatment changes, including reason for the change, will be recorded in the eCRF.
- Accountability of patches and Abilify MyCite product (aripiprazole tablet embedded with an IEM sensor) supplies performed.
- Review Abilify MyCite dashboard data every 2 weeks.
- [REDACTED]

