3.7.1.3.3 Month 3 Visit

Month 3 (- 3/ + 2 days) will be an investigator visit for the subject. At the Month 3 visit, the following will be performed:

- Administer the suicidality assessment (C-SSRS Since Last Visit Version; [Section 3.7.3.5](#)).
- Perform vital signs assessment ([Section 3.7.3.3](#)).
- Monitor AEs, including device-related nonserious AEs ([Section 5](#)).
- Abilify MyCite products (aripiprazole tablet embedded with an IEM sensor), supplies, and patches (prescribed dose is recorded) sufficient for 1 month will be dispensed. Any treatment changes, including reason for the change, will be recorded in the eCRF.
- Accountability of patches and Abilify MyCite product (aripiprazole tablet embedded with an IEM sensor) supplies performed.

Protocol 031-201-00301

- Review Abilify MyCite dashboard data every 2 weeks.
- [REDACTED]
- [REDACTED]
- [REDACTED]
- Healthcare utilization record evaluation ([Section 3.7.1.4](#)).
- [REDACTED]
- [REDACTED]
- [REDACTED]
- [REDACTED]

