3.8.3.3 Withdrawal of Consent

All subjects have the right to withdraw their consent from further participation in the trial at any time without prejudice. Subjects cannot withdraw consent for use of data already collected as part of the trial, but only for future participation. The investigator can also discontinue a subject's participation in the trial at any time if medically necessary. Unless the subject provides their written withdrawal of consent or there is other written documentation by the investigator confirming the subject's verbal intent to completely withdraw from the trial, subjects should be followed for all protocol-specified evaluations and assessments, if possible.

Complete withdrawal of consent requires a subject's refusal of all of the following methods of follow-up (these methods of follow-up will also be noted in the trial ICF):

- Participation in all follow-up procedures specified in the protocol (whether in-clinic, by telephone, or by an in-home visit).
- Participation in a subset of protocol-specified follow-up procedures (by a frequency schedule and method, as agreed by subject and staff).
- Contact of the subject by trial personnel, even if only by telephone, to assess current medical condition, and obtain necessary medical or laboratory reports relevant to the trial's objectives.

Protocol 031-201-00301

- Contact of alternative person(s) who have been designated in source records as being available to discuss the subject's medical condition, even if only by telephone, mail, or email (eg, family, spouse, partner, legal representative, friend, neighbor, or physician).
- Access to medical information from alternative sources (eg, hospital/clinic medical records, referring doctor's notes, public records, dialysis, transplantation or vital registries, social media sources).

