3.12 Subject Compliance

Subjects will be required to have at least 3 months of Abilify MyCite medication. Noncompliant subjects will be followed throughout the trial period and analysis will be performed as described in [Section 7.4](#). Discontinuation of noncompliant subjects is at the discretion of the investigator.

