5.1.3 Study Week/Month Windows

For all the efficacy analysis with two assessment at month 3 and month 6 including [redacted] healthcare utilization record evaluation, [redacted] [redacted], [redacted], analysis windows for Month 3 LOCF and Month 6 LOCF are defined as the last assessment within in the timeframe defined in [Table 5.1.3-1](#). [redacted]

[redacted] Healthcare utilization record evaluation, [redacted] [redacted]

will be performed for timepoints at Month 3 LOCF, Moth 6 LOCF and Last visit.

Table 5.1.3-1 Mapping of Trial Windows A	
Visit	Number of Trial Days in Each Phase
	Window (days)
Month 3	68- 97
Month 3 LOCF	1 – 97
Month 6	135 - 182
Month 6 LOCF	98 - 182

Protocol 31-201-301 Interim Analysis Plan

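### Protocol 3.7.1.3 lets the sponsor discontinue a subject over an out-of-window visit, with no exception for a psychiatric admission, so the primary event itself can lead to loss from the primary analysis set

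*Protocol*

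**What the plan says.** Protocol 3.7.1.3 sets the visit spacing ("Monthly assessments will follow a 28-day schedule") and the procedure for a missed visit. The site reschedules as near as it can to the planned date. Where the new date still misses the permitted range, the matter goes to the sponsor or its delegate, and the stated purpose is "to determine whether the subject can continue in the trial and to obtain approval to continue or discontinue the subject". The section does not say on what grounds the sponsor decides, and it makes no exception for a subject who was in hospital. The window is the same at Months 1 and 2 (3.7.1.3.2) and at Month 3 (3.7.1.3.3: "Month 3 (- 3/ + 2 days) will be an investigator visit for the subject"). Section 3.6 states that the trial is open-label and lists no other measure against bias.

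Other sections point towards keeping subjects under observation:

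- 3.8.3.3: short of complete withdrawal, "subjects should be followed for all protocol-specified evaluations and assessments, if possible".
- 3.12: "Noncompliant subjects will be followed throughout the trial period and analysis will be performed as described in" section 7.4.
- 3.8.3.1: the sponsor would like to follow subjects who elect to stop early for the full trial duration.

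Two definitions decide who enters the primary McNemar test. Protocol 7.2 builds the efficacy set from subjects who completed the first 3 months of dosing. SAP 5.1.1 requires at least 80% of study medication in the analysis period and complete hospitalization information, and SAP 7.1 makes that Month 1-3 mITT set the primary one.

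**The concern.** The primary endpoint is whether a subject had at least one inpatient psychiatric hospitalization in each period. An admission that spans a visit window can cause the missed visit, so the outcome can set off a sponsor decision about whether the subject stays in the trial. In an open-label trial the sponsor can know the reason when it decides.

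The retrospective period has no counterpart. It is taken from existing records, and an admission in it cannot end a subject's participation.

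The harm comes through the analysis set. The admission may be fully documented, yet a subject whose participation ends at Month 1 or 2 can miss the dosing requirement and so leave the primary comparison. Losing a subject hospitalized only in the prospective period removes a pair that counts against Abilify MyCite. Losing a subject hospitalized in both periods leaves the McNemar statistic unchanged. Loss by this route therefore cannot work against the product.

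**Working it through.** **1. The plan's own figure.** Protocol 7.1 gives p10 = 13.5% (hospitalized retrospectively only), p01 = 5% (prospectively only), marginal rates of 15.5% and 7%, and 200 completers for 80% power at two-sided 0.05. Hospitalized in both periods: 15.5 - 13.5 = 2%. Check: 2 + 5 = 7%.

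n = [1.96 × √0.185 + 0.8416 × √(0.185 - 0.085²)]² / 0.085² = 198.6, so 199. Power at 200 is 80.3%. The stated 200 is reproduced and is not disputed.

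**2. Window.** 3 + 1 + 2 = 6 calendar days, one window every 28 days.

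**3. Does discontinuation at Month 1 or 2 lead to exclusion?** The SAP's 80% of an 84-day period is 0.8 × 84 = 67.2 days. The Month 2 window closes at about Day 58, and 58/84 = 69%. If trial-supplied product stops with participation, a subject discontinued at Month 1 or 2 falls below 80%, and has not completed 3 months of dosing either. At Month 3 the dosing period is essentially over. Month 3 therefore adds to the chance of triggering the rule but much less to exclusion.

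**4. How often would a stay cover a whole window?** Assume admission days are uniform over 84 days and an inpatient cannot attend. A stay of L days covers all 6 window days for L - 5 admission days. Months 1 and 2: f = 2(L - 5)/84. With Month 3: 3(L - 5)/84 = (L - 5)/28.

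**5. Effect on the paired difference, upper bound.** If every subject counted under Months 1 and 2 is discontinued and excluded, a fraction f of the prospectively hospitalized 7% is lost:

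difference = [0.135 - 0.05(1 - f)] / (1 - 0.07f)

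| Stay (days) | f, Months 1-2 | With Month 3 | Paired difference (plan 8.5) |
|---|---|---|---|
| 10 | 12% | 18% | 9.2 points |
| 14 | 21% | 32% | 9.7 points |
| 21 | 38% | 57% | 10.7 points |

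For 14 days: f = 18/84 = 0.214; (0.135 - 0.0393)/(1 - 0.015) = 0.0957/0.985 = 9.7%. These are proportions, so the result does not depend on whether 224 completers or 320 enrolled is the base.

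**6. Illustration with no true effect.** Exact enumeration of the uncorrected McNemar test at 0.05, starting from 224 subjects, as a single look that ignores the interim boundaries:

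| Fraction of prospectively hospitalized lost | 15.5% in both periods, 18.5% discordant | 7% in both periods, 10% discordant |
|---|---|---|
| 0 | 4.9% | 5.3% |
| 10% | 6.2% | 5.9% |
| 20% | 10.3% | 8.1% |
| 30% | 18.1% | 12.1% |

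The fractions lost are assumptions, not predictions.

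**The case against.** Much of the case on the other side stands.

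- A reader might infer that an inpatient is likely to miss the window. The figures do not support that. Even counting all three windows, a stay must reach about 19 days for a 50% chance. The documents give no length of stay and do not say that an inpatient cannot be assessed.
- A reader might infer that the rule ends follow-up. It requires a consultation, and continuing is one of its two outcomes.
- A reader might infer that the admission goes unrecorded. Usually it would be recorded. Protocol 3.7.2.1.1 has hospitalizations reported continuously. Section 3.7.1.3.5 requires Month 6/ET evaluations, including the healthcare utilization review, for anyone withdrawn short of full withdrawal of consent. The admission behind the missed visit has already settled a yes/no endpoint.
- A reader might infer a flat contradiction within the protocol. In this protocol, being discontinued and being followed can coexist: 3.12 leaves discontinuation of noncompliant subjects to the investigator, 3.8.3.3 is qualified by feasibility, and the Day 14 rule in 3.8.3.1 ends participation yet continues follow-up. The wish for full-duration follow-up in 3.8.3.1 is worded for subjects who elect to stop. What is missing is any statement of which rule governs after a 3.7.1.3 decision.
- A reader might cite the SAP as already accepting late visits. SAP 5.1.3 says "analysis windows for Month 3 LOCF and Month 6 LOCF are defined as the last assessment within in the timeframe defined in" its table, and that table covers only Months 3 and 6. It has no window for Months 1 and 2, where product is dispensed for one month and a late visit raises a supply question.
- The SAP table list includes an ITT analysis of the primary endpoint (CT-5.1.2).

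Two things survive this. Recording the event does not put the subject back into the primary set, and the ITT table is not the primary analysis. The sensitivity analysis in SAP 7.1.3 is no help, since it restricts the mITT set further to 3-month completers.

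**Conclusion.** The point holds as a gap in the rule that can feed outcome-dependent exclusion from the primary test. Section 3.7.1.3 allows an open-ended sponsor decision that the primary event can trigger, and the primary set then drops a subject who stops early. The effect is confined to the prospective period and favours Abilify MyCite. With 14-day stays, Months 1 and 2 only, and every affected subject discontinued and excluded, the paired difference would be about 9.7 points instead of 8.5. That is an upper bound for that stay length. It rests on uniform admission days, an inpatient being unable to attend, and product stopping with participation. Nothing in the documents indicates what fraction would actually be discontinued, so they do not support saying that trial conduct alone will lower the Abilify MyCite rate. Sections 3.7.1.3, 3.8.3.1, 3.8.3.3 and 3.12 need to be reconciled. The change is worth making because it is small and the possible bias runs one way.

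**What to change.** In Protocol 3.7.1.3, state that an out-of-window visit is held as soon as possible, is recorded as a protocol deviation with its reason, and is not in itself grounds for ending trial follow-up. Add that hospitalization records are collected to Day 84 and Day 168 whatever the visit timing, unless consent is fully withdrawn.

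That alone does not keep the subject in the primary test. If trial product is not taken in hospital, 17 missed days are enough to fail the 80% rule (67 days taken, against 67.2 needed). So also state in Protocol 7.2 and SAP 5.1.1 that subjects with a known Months 1-3 hospitalization outcome who missed a visit because of an admission stay in the primary comparison. Failing that, report the already listed ITT analysis (CT-5.1.2) beside the primary result.

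Whether Abilify MyCite treatment or supply continues remains a clinical decision, and no change to it is proposed. The cost is a short protocol amendment and one line in the SAP. The downside is that some late visits stay in the data.

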3.7.1.3.1 Baseline (Day 1)

After completion of the screening visit assessments and procedures, the subject will return for the baseline visit.

At the baseline visit, the following will be performed:

- Obtain urine sample for pregnancy test (WOCBP; Section 3.7.3.2).
- Administer the suicidality assessment (C-SSRS Since Last Visit Version; Section 3.7.3.5).
- Perform vital signs assessment (Section 3.7.3.3).
- Monitor AEs, including device-related nonserious AEs (Section 5).
- Abilify MyCite system onboarding (Section 3.2.2.2).
- The following will be dispensed to the subject:
 - Abilify MyCite products (aripiprazole tablet embedded with an IEM sensor), supplies, and patches (prescribed dose is recorded) sufficient for 1 month (from baseline [Day 1] to Month 1).
 - Instructions on how to install the Abilify MyCite smartphone application.
 - User Guide for Abilify MyCite including introductory video and reference guides.
 - Contact information for the call center.

Protocol 031-201-00301

- The first dose of Abilify MyCite is to be taken at the baseline (Day 1) visit (in the clinic) during onboarding, unless they have already taken their daily dose. Subjects should not take their oral standard-of-care medication that morning before the baseline visit.
- Review subject and investigator dashboards with the subject.
- [REDACTED]
- [REDACTED]
- [REDACTED]
- [REDACTED]
- [REDACTED]
- [REDACTED]
- [REDACTED]

3.7.1.3.2 Months 1 and 2 Visits

At the Months 1 and 2 visits (- 3/ + 2 days), the following will be performed:

- Abilify MyCite products (aripiprazole tablet embedded with an IEM sensor), supplies, and patches (prescribed dose is recorded) sufficient for 1 month will be dispensed. Any treatment changes, including reason for the change, will be recorded in the eCRF.
- Accountability of patches and Abilify MyCite product (aripiprazole tablet embedded with an IEM sensor) supplies performed.
- Review Abilify MyCite dashboard data every 2 weeks.
- [REDACTED]

3.7.1.3.3 Month 3 Visit

Month 3 (- 3/ + 2 days) will be an investigator visit for the subject. At the Month 3 visit, the following will be performed:

- Administer the suicidality assessment (C-SSRS Since Last Visit Version; [Section 3.7.3.5](#)).
- Perform vital signs assessment ([Section 3.7.3.3](#)).
- Monitor AEs, including device-related nonserious AEs ([Section 5](#)).
- Abilify MyCite products (aripiprazole tablet embedded with an IEM sensor), supplies, and patches (prescribed dose is recorded) sufficient for 1 month will be dispensed. Any treatment changes, including reason for the change, will be recorded in the eCRF.
- Accountability of patches and Abilify MyCite product (aripiprazole tablet embedded with an IEM sensor) supplies performed.

Protocol 031-201-00301

- Review Abilify MyCite dashboard data every 2 weeks.
- [REDACTED]
- [REDACTED]
- [REDACTED]
- Healthcare utilization record evaluation ([Section 3.7.1.4](#)).
- [REDACTED]
- [REDACTED]
- [REDACTED]
- [REDACTED]

3.7.1.3.4 Months 4 and 5 Visits

At the Months 4 and 5 visits (- 3/ + 2 days), the following will be performed for subjects remaining on Abilify MyCite treatment:

- Abilify MyCite products (aripiprazole tablet embedded with an IEM sensor), supplies, and patches (prescribed dose is recorded) sufficient for 1 month will be dispensed. Any treatment changes, including reason for the change, will be recorded in the eCRF.
- Accountability of patches and Abilify MyCite product (aripiprazole tablet embedded with an IEM sensor) supplies performed.
- Review Abilify MyCite dashboard data every 2 weeks.

3.7.1.3.5 Month 6/Early Termination Visit

Month 6/ET (- 3/ + 2 days) will be an investigator visit for the subject. In addition, Month 6/ET visit evaluations are to be completed for any subject withdrawn from the trial at any time (for any reason other than full withdrawal of the consent). At the Month 6/ET visit, the following will be performed:

- Administer the suicidality assessment (C-SSRS Since Last Visit Version; [Section 3.7.3.5](#)).
- Perform vital signs assessment ([Section 3.7.3.3](#)).
- Monitor AEs, including device-related nonserious AEs ([Section 5](#)).
- Accountability of patches and Abilify MyCite product (aripiprazole tablet embedded with an IEM sensor) supplies performed for subjects remaining on Abilify MyCite treatment. Any treatment changes, including reason for the change, will be recorded in the eCRF.
- Review Abilify MyCite dashboard data every 2 weeks for subjects remaining on Abilify MyCite treatment.

Protocol 031-201-00301

- [REDACTED]
- [REDACTED]
- [REDACTED]
- [REDACTED]
- [REDACTED]
- [REDACTED]
- Healthcare utilization record evaluation ([Section 3.7.1.4](#)).
- [REDACTED]
- [REDACTED]
- [REDACTED]
- [REDACTED]

3.7.1.4 Healthcare Utilization Record Evaluation (Month -6 Through Month 6/ET)

Healthcare utilization record evaluation will take place 6 months prior to and following the baseline (Day 1) visit (for a total of 12 months) to evaluate the subject health records and to examine subject interaction with the investigators prior to and following usage of Abilify MyCite. All hospital admissions and number of days spent in an inpatient setting (psychiatric) would be recorded and assessed as either ‘planned’ or ‘unplanned’ and ‘related’ or ‘unrelated’ to the psychiatric illness. Similarly, all encounters between any investigators (psychiatric) and the subject will be recorded to obtain the following information:

- The nature of the contact (eg, office visit, partial hospitalization).
- The investigator role (eg, community psychiatric nurse).
- Whether the contact was planned or not.
- Whether or not the contact was initiated as a result of data from Abilify MyCite.
- Any medication titration, adherence counseling, education, and lifestyle coaching.

Intervention data includes psychiatric hospitalizations, outpatient visits, the number of crisis interventions, and pharmacy cost of all medications. This data will be recorded in the eCRF at Month 3 and Month 6/ET.

Protocol 031-201-00301

3.7.1.5 Follow-up

A follow-up phone call for subjects who conclude the study on Abilify MyCite will occur 30 days (\pm 3 days) after the Month 6/ET visit, which will be the last official subject contact. At this time, the investigator will review SAEs and device-related nonserious AEs and the subject and investigator dashboards with the subject.

3.7.2 Efficacy Assessments

Not applicable.

3.7.2.1 Other Trial Assessments

3.7.2.1.1 Hospitalization

Data on subject inpatient psychiatric hospitalizations and outpatient or non-inpatient psychiatric treatment visits will be continuously reported during the trial. This data will include number and mean duration of all other (non-inpatient) psychiatric treatment visits including, but not limited to hospitalizations, emergency department visits, partial hospitalization visits, intensive outpatient visits, assertive community treatment visits, outpatient visits for psychotherapy and/or medication management, etc.

This information will be captured on the eCRF.

[REDACTED]

Protocol 031-201-00301

[Redacted text block]

[Redacted text block]

[Redacted text block]

[Redacted text block]

[Redacted text block]

Protocol 031-201-00301

[Redacted text block]

- [Redacted list item]
- [Redacted list item]
- [Redacted list item]
- [Redacted list item]

[Redacted text block]

[Redacted text block]

[Redacted text block]

[Redacted text block]

Protocol 031-201-00301

3.7.3 Safety Assessments

3.7.3.1 Adverse Events

Refer to [Section 5](#), Reporting of AEs.

3.7.3.2 Clinical Laboratory Assessments

Urine pregnancy for WOCBP will be conducted at screening and Day 1. If deemed appropriate, serum pregnancy test will be performed if positive urine screen is detected. Additional clinical laboratory assessments will be performed at screening and at the investigator's discretion to ensure safety of the subject but are not required as part of this trial.

3.7.3.3 Vital Signs

Vital signs will be performed at screening, baseline (Day 1), Month 3, Month 6/ET, and at the investigator's discretion at subsequent visits to ensure safety of the subject but are not required as part of this trial.

3.7.3.4 Electrocardiogram Assessments

Electrocardiograms will be collected by the subjects at screening to confirm eligibility. Electrocardiogram recordings will be obtained after the subject has been at rest for at least 5 minutes. All ECGs will be reviewed by the investigator to assess normal from abnormal results. Any screening ECG with abnormal result(s) considered to be clinically significant can be repeated to confirm the finding(s) prior to excluding the subject.

3.7.3.5 Suicidality

Suicidality will be monitored throughout the trial using the C-SSRS.²² The C-SSRS was developed by a team of researchers at Columbia University to address the need for standardized classification of suicide reports to assess suicide risk. This scale consists of a baseline evaluation that assesses the lifetime experience of the subject with suicide events and suicidal ideation and a post-baseline evaluation that focuses on suicidality since the last assessment. The Baseline/Screening Version and the Since Last Visit version of the C-SSRS will be completed by trained trial site staff at the time points presented in the Schedule of Assessments [Table 3.7-1](#).

